3.4.3 Prohibited and/or Restricted Treatments

Any systemic, anti-myeloma therapy other than pomalidomide, dexamethasone, and elotuzumab are prohibited while on study therapy. Concomitant steroids, other than weekly dexamethasone [Section 4.5.1](#) or steroids allowed (as defined in eligibility criteria) are prohibited unless used to treat an adverse event. Guidelines for selection and use of other concomitant medications should be derived from the pomalidomide and dexamethasone prescribing information.

Avoid co-administration of pomalidomide with strong inhibitors of CYP1A2 unless medically necessary. Co-administration of pomalidomide with drugs that are strong inhibitors of CYP1A2 (eg, ciprofloxacin, enoxacin and fluvoxamine) and CYP3A4/5 (eg, ketoconazole) or P-gp could increase pomalidomide exposure and should be avoided, unless medically necessary^{43, 44}.

Other than study medications, administration of any therapeutic or diagnostic investigational agent (for any indication) is prohibited while on study therapy without prior Sponsor approval.

3.4.4 Surgery and Radiation

Use of radiotherapy or surgical intervention must be recorded on the appropriate Case Report Form.

Localized radiation therapy to a site of pre-existing disease may be permitted while on study. Following approval by the medical monitor, the patient may continue with protocol therapy without interruption during the course of palliative radiation therapy if the investigator believes that the risk of excessive bone marrow suppression or other toxicity is acceptable, and it is in the best interest of the patient to do so.

If the subject develops a definite increase in the size of existing bone lesions or soft tissue plasmacytomas that meets the criteria for disease progression ([Appendix 6](#)), treatment must be discontinued for progressive disease regardless of whether radiation therapy is initiated (Section 3.5).

Kyphoplasty, vertebroplasty, or emergency orthopedic surgery is permitted.

3.5 Discontinuation of Subjects following any Treatment with Study Drug

Subjects MUST discontinue investigational product (and non-investigational product at the discretion of the investigator) for any of the following reasons:

- Withdrawal of informed consent (subject's decision to withdraw for any reason)
- Any clinical adverse event (AE), laboratory abnormality or intercurrent illness which, in the opinion of the investigator, indicates that continued participation in the study is not in the best interest of the subject.
- Pregnancy (Subjects must discontinue elotuzumab and pomalidomide).
- Termination of the study by Bristol-Myers Squibb (BMS).
- Loss of ability to freely provide consent through imprisonment or involuntarily incarceration for treatment of either a psychiatric or physical (eg, infectious disease) illness.
- Progressive Disease ([Appendix 6](#))
- Subjects who receive any non-protocol specified systemic anti-myeloma therapy before documented progression will be discontinued from all study treatment (including pomalidomide/dexamethasone); however, tumor assessments will continue at 4 week intervals until documented progression.
- Subjects experiencing a Grade 4 infusion reaction must discontinue elotuzumab. Subjects may continue pomalidomide and dexamethasone treatment. Refer to [Section 4.5.2.3](#).
- Subjects experiencing angioedema, Grade 4 rash, exfoliative or bullous rash, Stevens-Johnson syndrome, or toxic epidermal necrolysis related to pomalidomide must discontinue pomalidomide. Subjects in the elotuzumab arm may continue elotuzumab and dexamethasone.
- Subjects experiencing a 56 day delay in all study drugs (pomalidomide, dexamethasone, and elotuzumab) due to an adverse event(s) related to study treatment must be discontinued from

study drug. Subjects experiencing delays unrelated to study therapy, for example due to radiation therapy, may delay study treatment up to 84 days. Further delays may be allowed after discussion with the BMS Medical Monitor. Delays greater than 28 days must be discussed with the medical monitor.

In the case of pregnancy, the investigator must immediately notify the BMS Medical Monitor/designee of this event. In most cases, the study drug will be permanently discontinued in an appropriate manner. If the investigator determines a possible favorable benefit/risk ratio that warrants continuation of study drug, a discussion between the investigator and the BMS Medical Monitor/designee must occur.

All subjects who discontinue study drug should comply with protocol specified follow-up procedures as outlined in [Table 5.1-3](#). The only exception to this requirement is when a subject withdraws consent for all study procedures or loses the ability to consent freely (ie, is imprisoned or involuntarily incarcerated for the treatment of either a psychiatric or physical illness).

If study drug is discontinued prior to the subject's completion of the study, the reason for the discontinuation must be documented in the subject's medical records and entered on the appropriate case report form (CRF) page.

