Study Drug: includes both Investigational [Medicinal] Products (IP/IMP) and Non-investigational [Medicinal] Products (Non-IP/Non-IMP) as listed:

Study Drug for CA204125		
Medication	Potency	IP/Non-IP
Elotuzumab	400mg/vial	IP
Pomalidomide Capsules	1 mg, 2 mg, 3 mg and 4 mg	Non-IP
Dexamethasone Tablets	2 mg and 4 mg & various strengths	Non-IP
Dexamethasone Solution	4 mg/mL, 8 mg/mL & various strengths	Non-IP

Study Assessments: Tumor response assessment by modified IMWG criteria ([Appendix 6](#)) will be evaluated during the trial for all randomized subjects. The primary endpoint of PFS will be based on the investigator’s assessment

Statistical Considerations:

[REDACTED]

[REDACTED]

[REDACTED]

[REDACTED]

[REDACTED]

[REDACTED]

[REDACTED]

Endpoints:

Primary Endpoint:

PFS will be defined as the time, in months, from randomization to the date of the first documented tumor progression or death due to any cause. Clinical deterioration will not be considered progression. A subject who neither progresses nor dies will be censored on the date of their last tumor assessment. A subject who does not have any post-baseline tumor assessments and who has not died will be censored on the date at which they were randomized.

Secondary Endpoint:

- 1) Objective response rate is defined as the proportion of randomized subjects who achieve a best response of partial response (PR) or better using the criteria in [Appendix 6](#) as per investigator's assessment.
- 2) Overall survival is defined as the time from randomization to the date of death from any cause. If a subject has not died, their survival time will be censored at the date of last contact ("last known alive date"). A subject will be censored at the date of randomization if they were randomized but had no follow-up.

[REDACTED]

[REDACTED]

[REDACTED]

[REDACTED]

[REDACTED]

[figure not shown]

[figure not shown]
[figure not shown]
[figure not shown]

[REDACTED]

[figure not shown]
[REDACTED]

[REDACTED]

TABLE OF CONTENTS

[figure not shown]
TITLE PAGE 1
DOCUMENT HISTORY 3
SYNOPSIS 4
TABLE OF CONTENTS 9
[REDACTED] 13
[REDACTED] 13
[REDACTED] 13
[REDACTED] 13
[REDACTED] 13
[REDACTED] 13
[REDACTED] 15
[REDACTED] 18
[REDACTED] 19
[REDACTED] 20
[REDACTED] 21
[REDACTED] 21
[REDACTED] 23
[REDACTED] 23
[REDACTED] 25
[REDACTED] 25
[REDACTED] 27
1.2 Research Hypothesis 28
1.3 Objectives(s) 28
 1.3.1 Primary Objectives 28
 1.3.2 Secondary Objectives 28
[REDACTED] 29
[REDACTED] 29
[REDACTED] 29
[REDACTED] 30

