4 STUDY DRUG

All protocol-specified investigational and non-investigational products are considered study drug

Table 4-1: Study Drugs for CA204125					
Product Description / Class and Dosage Form	Potency	IMP/Non-IMP	Blinded or Open Label	Packaging / Appearance	Storage Conditions (per label)
Elotuzumab Powder for Solution for Infusion	400 mg/vial	IMP	Open Label	20 mL Vial/ Sterile, white to off-white, preservative-free, lyophilized cake	Store at 2°C - 8°C
Dexamethasone Tablets	2 mg and 4 mg & various strengths	Non-IMP	NA	Various packing configurations	Refer to label on container or package insert / summary of product characteristics
Dexamethasone Solution	4 mg/mL, 8 mg/mL & various strengths	Non-IMP	NA	Various packing configurations	Refer to label on container or package insert / summary of product characteristics
Pomalidomide Capsules	1 mg, 2 mg, 3 mg and 4 mg	Non-IMP	Open label	Various packing configurations	Refer to label on container or package insert

Dexamethasone tablets and solution for IV infusion may be obtained by the investigating site’s standard prescribing procedures. Pomalidomide (Pomalyst[®]) may be supplied by BMS centrally or through site standard prescribing procedure.

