6.4 Pregnancy

If, following initiation of the study drug, it is subsequently discovered that a study subject is pregnant or may have been pregnant at the time of study exposure, including during at least time to washout (90 days) plus one ovulatory cycle (30 days) for a total of 120 days, or plus one spermatogenesis cycle (90 days) for a total of 180 days after product administration, the investigator must immediately notify the BMS Medical Monitor/designee of this event and complete and forward a Pregnancy Surveillance Form to BMS Designee within 24 hours of awareness of the event and in accordance with SAE reporting procedures described in [Section 6.1.1](#).

In most cases, the study drug will be permanently discontinued in an appropriate manner (eg, dose tapering if necessary for subject safety).

In the rare event that the benefit of continuing study drug is thought to outweigh the risk, after consultation with BMS, the pregnant subject may continue study drug after a thorough discussion of benefits and risk with the subject

Protocol-required procedures for study discontinuation and follow-up must be performed on the subject unless contraindicated by pregnancy (eg, x-ray studies). Other appropriate pregnancy follow-up procedures should be considered if indicated.

The investigator must immediately notify the BMS (or designee) Medical Monitor of this event and complete and forward a Pregnancy Surveillance Form to BMS (or designee) within 24 hours of awareness of the event and in accordance with SAE reporting procedures described in [Section 6.1.1](#).

Follow-up information regarding the course of the pregnancy, including perinatal and neonatal outcome and, where applicable, offspring information must be reported on the Pregnancy Surveillance Form.

Any pregnancy that occurs in a female partner of a male study participant should be reported to BMS. Information on this pregnancy will be collected on the Pregnancy Surveillance Form.

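### Protocol Section 3.5 makes pregnant subjects stop elotuzumab and pomalidomide, but Section 6.4 lets a pregnant subject continue study drug, a term defined to include both

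*Protocol*

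**What the plan says.** Three parts of the protocol bear on the point.

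- **Section 3.5, discontinuation list.** The lead-in makes stopping investigational product mandatory and leaves non-investigational product to the investigator. The pregnancy entry then names two drugs: "Pregnancy (Subjects must discontinue elotuzumab and pomalidomide". It gives no exception.
- **Section 3.5, closing paragraph on pregnancy.** This is softer: "In most cases, the study drug will be permanently discontinued in an appropriate manner". If the investigator sees a possible case for continuing, "a discussion between the investigator and the BMS Medical Monitor/designee must occur".
- **Section 6.4.** The default is "In most cases, the study drug will be permanently discontinued in an appropriate manner (eg, dose tapering if necessary for subject safety". The exception opens with "In the rare event that the benefit of continuing study drug is thought to outweigh the risk" and goes on: "after consultation with BMS, the pregnant subject may continue study drug after a thorough discussion of benefits and risk with the subject".

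The term study drug is defined twice. The synopsis has "Study Drug: includes both Investigational [Medicinal] Products (IP/IMP) and Non-investigational [Medicinal] Products (Non-IP/Non-IMP) as listed", above a table of elotuzumab, pomalidomide and dexamethasone (tablets and solution). Section 4 has "All protocol-specified investigational and non-investigational products are considered study drug".

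**The concern.** One section imposes an unconditional stop on two named drugs. The other allows continuation of a defined set that contains both of them. The answer to whether a pregnant subject may stay on pomalidomide then depends on which section is opened.

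A site dealing with a pregnancy would naturally turn to Section 6.4, which carries the notification and reporting steps. That section neither repeats the mandatory stop nor refers back to Section 3.5; its visible cross-references go to Section 6.1.1.

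What is at stake is fetal exposure. Section 4.2.1 describes pomalidomide as an analogue of thalidomide, warns that taking it in pregnancy may cause birth defects or fetal death, and says females must not become pregnant while on it.

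**Working it through.** The plan gives no figure to reproduce, so the check sets the texts side by side and counts the drugs that could remain.

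**Step 1: the two rules.**

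| | Section 3.5, pregnancy entry | Section 6.4, exception |
|---|---|---|
| Force | Must stop | May continue |
| Drugs | Elotuzumab and pomalidomide, by name | Study drug, none named or excluded |
| Conditions | None | Rare case, favourable benefit/risk, sponsor consulted, discussion with the subject |

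The conditions in Section 6.4 restrict when the exception applies. They do not restrict which drugs it covers, so they do not reconcile it with an unconditional stop.

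**Step 2: the defined term.** Section 4.1 makes elotuzumab the investigational product. Section 4.2 places pomalidomide and dexamethasone among the non-investigational products. Both definitions of study drug take in both classes. Section 3.5 uses the term the same way: its rule on 56-day delays lists pomalidomide, dexamethasone and elotuzumab as the study drugs.

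**Step 3: drugs that may remain in pregnancy** (counting the drugs in the study drug table).

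- Elotuzumab arm (3 drugs): Section 3.5 entry, 3 − 2 = 1 (dexamethasone). Section 6.4 read literally, up to 3.
- Control arm (2 drugs): Section 3.5 entry, 2 − 1 = 1 (dexamethasone). Section 6.4 read literally, up to 2.

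**Step 4: does Section 3.5 settle the matter itself?** Not fully. Its closing paragraph grants no permission, since it only requires a discussion. But by describing discontinuation as what happens in most cases, it treats as open something the list entry has already closed for two drugs.

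**Step 5: how Section 3.5 handles partial continuation elsewhere.** After a Grade 4 infusion reaction it names pomalidomide and dexamethasone as the drugs that may go on. After severe rash related to pomalidomide it names elotuzumab and dexamethasone. The pregnancy exception names none, so a reader cannot infer from the protocol's own pattern that it means dexamethasone alone.

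**The case against.** The strongest reply is that the sections can be read together. The Section 3.5 lead-in leaves non-investigational product to the investigator, and the pregnancy entry removes that discretion for pomalidomide. Only dexamethasone is left for any exception to govern, and a specific rule naming two drugs would ordinarily control a general one. Section 4.5.3 counts a subject taking only dexamethasone as still on study therapy. The tapering example in Section 6.4 does not fit elotuzumab, for which Section 4.5.4.1 allows no dose reduction. Section 6.4 also requires discontinuation and follow-up procedures unless pregnancy contraindicates them, which supports stopping as the default.

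This makes the dexamethasone-only reading plausible, and it may be what was intended. But no visible sentence says so. It also fits awkwardly: if the exception concerned only dexamethasone, Section 6.4 would demand sponsor consultation for a decision that the Section 3.5 lead-in already gives the investigator.

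The second reply is that continued exposure is improbable. Pomalidomide is dispensed only to subjects meeting every condition of the local risk program or the Prevention Plan, one cycle at a time. Pregnancy tests are scheduled, two contraceptive methods are required, and nobody may continue under Section 6.4 without consulting the sponsor. Appendix 8, the Pomalidomide Pregnancy Risk Prevention Plan, was not available for review and may hold an explicit stop rule. All of this stands and lowers the risk. It leaves the disagreement between Section 6.4 and the Section 3.5 entry where it was, even if Appendix 8 does contain such a rule.

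**Conclusion.** The concern holds. As written, Section 6.4 permits continuation of two drugs that the Section 3.5 entry requires to be stopped. The difference is one drug remaining (dexamethasone) against up to three in the elotuzumab arm, or up to two in the control arm.

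The documents do not say how many of the 114 planned subjects are women of childbearing potential, so the number who could be affected cannot be estimated; we assume it is very small. Alpha, power, sample size and the efficacy analyses are untouched.

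The conclusion rests on giving study drug its defined meaning and on the visible text alone. Because this is an operative safety rule for a drug with teratogenic risk, it should be corrected even though exposure is unlikely.

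**What to change.** In Section 6.4, replace the sentence on discontinuing in most cases and the sentence allowing continuation with text such as:

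> *Elotuzumab and pomalidomide must be permanently discontinued in pregnancy (Section 3.5). Continuation on a benefit/risk judgment, after consultation with the sponsor and discussion with the subject, applies only to dexamethasone.*

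Make the same restriction in the closing paragraph of Section 3.5, keeping the immediate notification and the Medical Monitor discussion. Check that Appendix 8 agrees.

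The cost is a wording change in two sections, by amendment or by administrative letter with notice to the ethics committees (Section 9.1.1), plus the appendix check. Sample size, data collection and analysis do not change.

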3.6 Post Study Drug Study Follow up

PFS and OS are key endpoints of the study. Post treatment study follow-up is essential to preserving subject safety and the integrity of the study. Subjects who discontinue study treatment prior to progression must continue to be followed for collection of protocol-defined PFS. Subjects who discontinue study therapy must also continue to be followed for overall survival data until death or the conclusion of the study.

BMS may request that survival data be collected on all randomized subjects outside of the protocol defined window, [Table 5.1-3](#). At the time of this request, each subject will be contacted to determine their survival status unless the subject has withdrawn consent for all contact.

3.6.1 Withdrawal of Consent

Subjects should be encouraged to continue participation in the trial until the laboratory definition of disease progression is met ([Appendix 6](#)). **Subjects who discontinue study therapy before progression (eg, due to toxicity) should be encouraged to allow the necessary laboratory results (eg, M-protein data, sFLC data, radiologic data, calcium results) to be collected until disease progression criteria are fulfilled, even if the subject is on subsequent therapy (see [Section 8.3.1](#)).** Central laboratory assessments are preferred; however assessments may also be completed locally. Local lab data can be obtained by the subjects' local health care provider or the site staff. Site staff will enter local lab data into the CRF/database. Withdrawal of consent should be minimized because:

1. The subject in this trial who discontinues study therapy before progression will most likely be followed by a healthcare provider locally or at the site via routine standard of care assessments (ie, monthly M-protein data, calcium, etc) and

2. In most cases, this protocol would not require any additional samples beyond those considered standard of care.

If there is uncertainty about the disease progression criteria, investigators are encouraged to contact the BMS Medical Monitor/study director prior to:

1. starting a subject on another myeloma regimen or
2. performing the end of treatment visit for progression

Subjects who request to discontinue study drug will remain in the study and must continue protocol specified follow-up procedures. The only exception to this is when a subject specifically withdraws consent for any further contact with him/her or persons previously authorized by subject to provide this information. Subjects should notify the investigator of the decision to withdraw consent from future follow-up **in writing**, whenever possible. The withdrawal of consent should be explained in detail in the medical records by the investigator as to whether the withdrawal is from further:

1. Study medication but subject is willing to continue to perform visits for PFS follow-up.
2. Study medication and study visits for PFS but agrees to provide the results of future myeloma assessments from another site/local site.
3. Study treatments and results from another site/local sites, but agrees to be contacted for overall survival follow-up.
4. Study treatments and results from another site/local sites, and does not agree to be contacted for overall survival follow-up.

In the event that vital status (whether the subject is alive or dead) is being measured, publicly available information should be used to determine vital status only as appropriately directed in accordance with local law

3.6.2 Lost to Follow-Up

All reasonable efforts must be made to locate subjects to determine and report their ongoing status. This includes follow-up with persons authorized by the subject as noted above. Lost to follow-up is defined by the inability to reach the subject after a minimum of three documented phone calls, faxes, or emails as well as lack of response by subject to one registered mail letter. All attempts should be documented in the subject's medical records. If it is determined that the subject has died, the site will use permissible local methods to obtain the date and cause of death.

If investigator's use of third-party representative to assist in the follow-up portion of the study has been included in the subject's informed consent, then the investigator may use a Sponsor-retained third-party representative to assist site staff with obtaining subject's contact information or other public vital status data necessary to complete the follow-up portion of the study. The site staff and representative will consult publicly available sources, such as public health registries, obituary listings, and databases, in order to obtain updated contact information.

If after all attempts, the subject remains lost to follow-up, then the last known alive date as determined by the investigator should be reported and documented in the subject's medical records

4 STUDY DRUG

All protocol-specified investigational and non-investigational products are considered study drug

Table 4-1: Study Drugs for CA204125					
Product Description / Class and Dosage Form	Potency	IMP/Non-IMP	Blinded or Open Label	Packaging / Appearance	Storage Conditions (per label)
Elotuzumab Powder for Solution for Infusion	400 mg/vial	IMP	Open Label	20 mL Vial/ Sterile, white to off-white, preservative-free, lyophilized cake	Store at 2°C - 8°C
Dexamethasone Tablets	2 mg and 4 mg & various strengths	Non-IMP	NA	Various packing configurations	Refer to label on container or package insert / summary of product characteristics
Dexamethasone Solution	4 mg/mL, 8 mg/mL & various strengths	Non-IMP	NA	Various packing configurations	Refer to label on container or package insert / summary of product characteristics
Pomalidomide Capsules	1 mg, 2 mg, 3 mg and 4 mg	Non-IMP	Open label	Various packing configurations	Refer to label on container or package insert

Dexamethasone tablets and solution for IV infusion may be obtained by the investigating site’s standard prescribing procedures. Pomalidomide (Pomalyst[®]) may be supplied by BMS centrally or through site standard prescribing procedure.

